7.4.5.8 SICCA Ocular Surface Staining

The sequence of staining of the ocular surface is important for its reproduction and accuracy. The application of fluorescein should be done before the application of lysmine green.

Fluorescein (TF) staining: A drop of topical anesthetic will be instilled in the bottom of the conjunctival sac, then a second drop will be applied to the tip of the fluorescein strip, allowing it to sit on the strip for 5 seconds to elute the dye, shaking off the excess at the end. A small contact of the strip is made with the conjunctiva at the fundus of the temporal sac, while the patient looks upwards, without damaging the conjunctiva. After evaluating the TRPL, between 4 and 8 minutes after the instillation of the stain, the evaluation of the fluorescein stain in the cornea is performed, with the slit lamp with a cobalt blue filter. It will be graded according to the Sjögren International Clinical Collaboration Alliance (SICCA) Eye Staining Rating (CTO). [43]

According to the CTO, grade 0 corresponds to the absence of punctate epithelial erosions (PES); grade 1 is defined as the presence of 1-5 EEP; grade 2 corresponds to 6-30 EEP; and >30 EEP will be classified as grade 3. Additionally, one rating point will be added if: 1) EEP is present in the central portion of the cornea with a diameter of 4mm; 2) filaments are observed and 3) confluent staining patches are observed, including linear stains. See Figure 2. [43]

The PI will record in the file and the eCRF the grade granted for the corneal staining of OD and OS, respectively. The maximum score per eye is 6.

Lysmine green (TVL) staining: After revision with fluorescein, a drop of saline solution will be applied to the tip of the lysmine green strip allowing it to sit on the strip for 5 seconds to elute the dye. A drop of the strip is instilled at the bottom of the temporal sac, while the patient looks upwards,

without damaging the conjunctiva. The patient may be asked to blink repeatedly to prevent accumulations in the conjunctival folds. The examination should be done between 1 and 4 minutes after installation through a neutral density filter or with the red-free filter. It will be graded according to the CTO of the SICCA. [43]

In CTO, grade 0 is defined as the presence of 0 to 9 spots of lysmine green staining in the interpalpebral bulbar conjunctiva (grading the temporal and nasal portion separately); grade 1 is defined by the presence of 10 to 32 points; grade 2 by 33 to 100; and grade 3 for >100 points. Due to the difficulty in counting individual points in a moving eye, any area $\geq 4\text{mm}^2$ of confluent points is considered >100 points. See Figure 2. [43]

The PI will record, in the file and in the eCFR, the sum of the grades given to the temporal and nasal portion for the OD, then the same evaluation will be performed in the OI and its record only in the clinical file. The maximum score per eye is 6.

[figure not shown]

Figure 1. SICCA Eye Staining Rating (Modified from Whitcher et al, 2010) [38]

Ocular surface staining by SICCA assessment is determined by the sum of corneal fluorescein staining and conjunctival staining with lysismine green. As seen in Figure 2. The values that can be obtained for each eye are from 0 to 12, and abnormal staining is considered when the value is 3 or greater.

Management as an EA: It will be considered an adverse event when the grade is greater than or equal to 3 points.

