7.4.5.5 Pupillary diameter

It is the hole in the middle of the iris through which light penetrates the eyeball. Its diameter results from the balance between the pupil sphincter muscle and the radial fibers of the iris (pupil dilator). Normal values are 2-6 mm. [37]

In higher concentrations this product is mydriatic, however, due to the nature of the research and the physicochemical characteristics this reaction is not expected to occur, we will consider as significant the change that is generated in the pupil of the research subjects > 2 mm (pharmacological mydriasis), whether this change in photopic or mesopic vision. The method to perform the measurement will be using the following tool: OPD-Scan III (NIDEK CO., LTD, Tokyo, Japan). It is requested that the tool used be the same for all patients of the research center and for all their visits. It is necessary that the measurement is always done in the same office, with the same artificial light conditions and that the patient has at least 5 minutes inside the place before the measurement.

If there is a change greater than 2 mm between baseline and any of the other measurements, the product will be considered to have produced pharmacological mydriasis. This change will also be considered an adverse event.

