7.4.5.6 Best-corrected visual acuity

Visual acuity (VA) is a test of visual function. Visual spatial acuity is the ability to distinguish separate elements of an object and identify them. It is quantified as the minimum angle of separation (located at the nodal point of the eye) between two objects that allow them to be perceived as separate objects.

Snellen's notation is described as the distance at which the test is performed, divided by the distance at which the letter is vertically equivalent to 5 arc minutes. Thus, at 6 meters a letter 6/6 (20/20) is equivalent to 5 minutes of arc, a letter 6/12 (20/40) is equivalent to 10 minutes, and a letter 6/60 (20/200) is equivalent to 50 minutes. The Snellen fraction can also be expressed as a decimal place (i.e., 20/20 = 1 and 20/40 = 0.5). [34]

VA will be evaluated at baseline, without refractive correction with the Snellen chart. It will be in a place with adequate lighting (natural or artificial) and at 3m from the subject to be evaluated. Visual acuity of the right eye will be taken initially, asking the subject to hold both eyes open and using an occlude to cover the contralateral eye; the subject will read aloud the lines that the evaluator points out, the line of smaller letters that he can see will be noted by the evaluator in fraction as the AV of OD in the clinical record and the eCRF, then the same evaluation will be performed in the left eye and its record only in the clinical file.

Next, the subject's best refractive correction (obtained by autokeratometer and subjective tests) will be evaluated and the examination will be repeated using the refraction obtained. This result will be reported as best-corrected visual acuity, both data will be reported for statistical purposes in logarithmic figures (LogMAR) and in eCRF.

A fraction conversion table is attached to LogMAR. (see annex 16.4 Fraction to LogMAR conversion table.)

Management as AE: A decrease in 2 or more lines of sight in BCVA compared to that obtained at baseline will be considered an adverse event.

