8.2 Definition of Adverse Event

According to the International Council on Harmonization (ICH), an adverse event (AE) is any unfavorable medical appearance in a clinical investigational subject who is administered a pharmaceutical product, regardless of causal attribution. [47] [48] [49]

Therefore, an AE can be any of the following: any unfavorable and unintentional disease, symptom, or sign (including an abnormal laboratory finding) that is temporally related to the use of a medical product, whether or not it is considered related to such a product; any new illness or exacerbation of an existing disease (worsening of the nature, frequency, or severity of a known condition); relapse of an intermittent medical condition (e.g., headache) not present at baseline; any deterioration in a laboratory value or other clinical test (e.g., electrocardiogram [ECG], x-ray) that is related to symptoms or that results in a change in study treatment or concomitant treatment or discontinuation of study medication. [47] [48] [49]

As defined in the previous paragraph, an adverse event is defined as any event that occurs during treatment with a drug or device. However, the definition can also be applied as any unwanted event that occurs during a clinical trial, including behavioral disorders. [49]

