8.5.2.6 Pre-existing medical conditions

A pre-existing medical condition should be recorded as AE only if the frequency, severity, or characteristics of the condition worsen during the study.

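### The staining rule makes any SICCA score of 3 or more an adverse event whatever the baseline score, while section 8.5.2.6 counts a pre-existing condition only if it worsens

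*Combined protocol and SAP*

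**What the plan says.** Section 7.4.5.8 adds corneal fluorescein and conjunctival green staining into a score from 0 to 12 per eye and calls 3 or more abnormal. The AE rule uses the same cut-off: "It will be considered an adverse event when the grade is greater than or equal to 3 points". Baseline is not mentioned.

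Section 8.5.2.6 takes the opposite approach to findings already present at entry: "A pre-existing medical condition should be recorded as AE only if the frequency, severity, or characteristics of the condition worsen during the study". The general definition in section 8.2 agrees with it and describes exacerbation as "worsening of the nature, frequency, or severity of a known condition".

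The AE rules for the other eye measures are protected in one of two ways:

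- **Relative to baseline.** For distance acuity (7.4.5.6): "A decrease in 2 or more lines of sight in BCVA compared to that obtained at baseline will be considered an adverse event". Near acuity (7.4.5.7) has the same form. For the pupil (7.4.5.5): "If there is a change greater than 2 mm between baseline and any of the other measurements".
- **Absolute, but limited at entry.** IOP is an AE from 24 mmHg (7.4.5.1), and section 5.1.1 admits only 10 to 21 mmHg. Heart rate and blood pressure have fixed AE limits, and 5.1.1 requires normal vital signs.

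Staining is measured at baseline, Visit 1 and the final visit (7.6.2, 7.7). Neither list in section 5.1 sets a limit for it. Its reference value in the table of variables (7.4.4) is 0 to 12, which is the whole scale.

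**The concern.** An AE count should reflect what happens after exposure. An absolute threshold does this only if nobody can start above it. That holds for IOP and vital signs, and the acuity and pupil rules reach the same end by using change from baseline. Staining has neither protection, so the rule can report a subject's entry status as an event on treatment.

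Two features make this worth settling. The study has one arm, so no control group would show how much staining is background. And AEs are also assessed at the baseline visit (7.6.2, 7.7.1), so a literal reading of 7.4.5.8 could record a staining AE before any dose.

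What is at stake is the overall AE incidence. The table of variables in 7.4.4 says that all AEs are reported, not only those suspected to be related. Two staff members following different sections would produce different counts from the same eyes.

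**Working it through.** **1. The two rules side by side.** Each row gives a subject's baseline score, a later score, and how each rule treats it. The last column is the rule proposed under the fix.

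| Baseline | Later | 7.4.5.8 as written | 8.5.2.6 | Proposed |
|---|---|---|---|---|
| 0 | 3 | AE | new finding, not pre-existing | AE |
| 3 | 5 | AE | AE (worse) | AE |
| 3 | 3 | AE | not an AE | not an AE |
| 5 | 3 | AE | not an AE (better) | not an AE |
| 0 | 2 | threshold not reached | not applicable | threshold not reached |

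The sections conflict in the third and fourth rows: staining that is stable or improving but still at 3 or more.

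**2. The number of subjects.** Section 10.1.2 takes 24 subjects and adds 20%: 24 × 1.20 = 28.8, rounded up to 29. The plan's figure reproduces.

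**3. Illustrative size.** Let q be the share of subjects who start at 3 or more and stay there. The documents give no value for q, so the values below are assumptions. Stable staining adds an expected 29q AEs under 7.4.5.8, and the chance of at least one is 1 − (1 − q)^29.

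| q (assumed) | Expected AEs, 29q | Chance of at least one |
|---|---|---|
| 2% | 29 × 0.02 = 0.58 | 1 − 0.98^29 = 0.44 |
| 5% | 29 × 0.05 = 1.45 | 1 − 0.95^29 = 0.77 |
| 10% | 29 × 0.10 = 2.90 | 1 − 0.90^29 = 0.95 |

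Under 8.5.2.6 the same subjects add 0 AEs at every value of q.

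**4. Which endpoint is reached.** The primary safety variable requires the AE to be both product-related and unexpected (7.4.1, 7.4.4). The secondary AE variable also requires relatedness (7.4.2). Section 8.5.4 ties relatedness to a plausible time sequence and a logical link between intervention and event. Staining that was there before the first drop and has not changed would rarely satisfy this. What remains is the all-AE tabulation.

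**The case against.** The best defence is that section 8 already governs. Section 7.4.5.9 sends AE management to section 8, which contains 8.5.2.6. On that reading 7.4.5.8 only defines abnormality, and section 8 decides whether a pre-existing abnormality is recorded. This is plausible and may be what was intended, but the documents do not say so. Staining is a named study variable with its own explicit AE rule.

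Section 7.4.5.9 also lets the investigator decide which examination findings are entered as AEs. That sentence closes a description of the comprehensive examination, whose procedures are described as lying outside the study variables. It does not clearly cover staining. If it did, the count would depend on individual judgement.

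A second defence is the population: healthy adults aged 18 to 35, without contact lens history, topical eye products, eye surgery or active inflammation. Scores of 3 or more may be rare, and an investigator might decline to enrol such a subject. This stands as a reason to expect a small effect. It does not remove the conflict, because the listed criterion requires only that subjects be clinically healthy, and no item mentions staining.

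It is also fair to say that an absolute threshold is a legitimate choice, and that other variables here use one. Those variables, however, are limited at entry.

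**Conclusion.** The inconsistency is real and rests on the text alone. Its consequence is modest: overall AE incidence may be inflated by stable or improving pre-existing staining, by an amount the documents do not allow anyone to estimate. The figures of 0.6 to 2.9 AEs among 29 subjects depend on the assumed 2% to 10%, on those scores persisting, and on sites following 7.4.5.8 literally.

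Two stronger readings are tempting and are not supported.

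- A reader might infer that the primary safety conclusion is at risk, since 3 of 29 is 10.3% and exceeds the 10% limit. That would need each case to be judged both related and unexpected. The first is unlikely for unchanged staining that predates dosing. The second is not automatic: staining is not named in the list of expected events, but dry eye, irritation and hyperemia are, and section 8.5.2.1 prefers a diagnosis to a sign.
- A reader might infer that a rise from 0 to 2 can never be an AE. Section 7.4.5.8 makes 3 or more an AE but does not forbid recording a lower score under section 8.2 or 8.3. Such a change is also seen in the exploratory staining analysis.

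This is a worthwhile clarification, not a threat to the study's main result.

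**What to change.** Reconcile 7.4.5.8 with 8.5.2.6 by adding one condition to the staining rule: a post-baseline SICCA score of 3 or more is recorded as an AE only when it is higher than the same subject's recorded baseline score. A cross-reference to 8.5.2.6 would make the intention plain. Limiting the rule to post-baseline scores also removes the possibility of a staining AE at the baseline visit itself.

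Worsening that stays below 3 is not addressed by this clause. It remains in the exploratory analysis of change in staining.

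The cost is one clause. The baseline score is already collected, no procedure is added, and only AE recording changes. It should be settled before data are recorded, because in an open-label single-arm study a later choice between the two rules would be made with the counts in view.

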7.4.5.9 Adverse events

As described in the 8. Evaluation and management of adverse events An adverse event is defined as any unfavorable medical occurrence in a subject to whom an investigational product is administered, regardless of causal attribution.

Adverse event management shall be carried out as described in section 8. Evaluation and management of adverse events and incidents.

The Principal Investigator will record in the corresponding section of the eCRF the adverse events that the study subjects may present in addition to referring them in the clinical record.

For an adequate evaluation of adverse events, in addition to directed questioning, it is necessary to perform a comprehensive ophthalmological evaluation at each visit, which consists of ophthalmological examination of the eyelids and adnexa; anterior and posterior segment that is performed in a routine ophthalmological check-up, whose procedures are not specifically included in the study variables. Posterior pole evaluation can be with direct or indirect ophthalmoscopy, with or without pharmacological mydriasis, at the discretion of the PI. An assessment of the fundus will be carried out in search of abnormalities that alter the result of the study. IOP will be measured in this evaluation, with the PI choice instrument, it should be measured after the evaluation of stains. The result of the assessment will be recorded in the clinical file. In the eCRF, only findings that are considered so by the Principal Investigator will be reported as an adverse event.

The adverse events that can occur with PRO-201 according to what is reported in the literature are: photophobia, mydriasis, difficulty reading, ocular allergic reactions (atopic dermatitis, allergic conjunctivitis and other allergic reactions), eye irritation, eye burning, eye pain, tearing, foreign body sensation, dry eye, hyperemia and/or red eye, blurred vision, eye itching; Systemic adverse events include: headache, drowsiness, dizziness, tachycardia, flushing, restlessness, irritability, dry skin, dry mouth, skin rash and decreased state of alert. [8] [6] [18] [19] [20] [21] [22] [23] [24]

7.4.5.10 Respiratory rate

It is the measurement of the breaths per minute that the subjects have per research. It is discreetly evaluated by observing, without the subject being aware of it, the movements of the rib cage, counting as one breath each increase/elevation of the subject's rib cage. 12 to 24 breaths per minute is considered normal.

Management as AE: Any value outside of the normal will be considered an adverse event. It is possible that in some cases the research subject should be considered as a possible case of a patient with COVID-19, and the investigator should refer the patient to medical attention and withdraw the subject from the investigation.

7.4.5.11 Body temperature

It is the degree or thermal level of a body. Normal values range from 35°C to 37.4°C. It can be taken by a contact thermometer or not, in different parts of the body. In the study, any thermometer calibrated at the research center may be used, if the same one is used for all patients and for all their visits.

Management as AE: Any value outside of the normal will be considered an adverse event. It is possible that in some cases the research subject should be considered as a possible case of a patient with COVID-19, and the investigator should refer the patient to medical attention and withdraw the subject from the investigation.

7.4.5.12 Ocular comfort index

It is a questionnaire designed to measure ocular surface irritation with Rasch analysis to produce estimates on a linear interval scale (ratings: 0-100). Like the index for ocular surface diseases, the ocular comfort index (OCI) assesses symptoms. The OCI contains 8 items (one positive and eight negative) that focus on discomfort associated with ocular surface alterations. Each of these questions has two parts, which separately inquire about the frequency and severity of symptoms. [44]See annex 16.3 Ocular Comfort Index (OCI)

At the baseline visit and final visit, the evaluator will deliver the questionnaire to the subject and allow the subject to answer it calmly without any pressure and/or coercion, only assisting him if he has difficulty understanding any of the questions.

7.5 Description of procedures or assessments during the study

The different procedures that will be done during the study are described below. The list may not be in order, and it may be arranged in the most optimal way according to the needs of the research center.

7.5.1 Signing of informed consent

Procedure by which it is guaranteed that the subject under investigation has voluntarily expressed his intention to participate in this research, after having understood the information that has been given to him about the objectives of the research, benefits, discomforts, and possible risks.

7.5.2 Preparation of medical history (includes ophthalmological and general medical history)

It must be carried out in accordance with the provisions of NOM-004-SSA3-2012 of the clinical file. Considering that the clinical record is the unique set of information and personal data of a patient, which is integrated into any type of establishment for medical care, whether public, social or private, which consists of written, graphic, imaging, electronic, magnetic, electromagnetic, optical, magneto-optical and any other type of documents, in which, Health personnel must make the records, annotations, where appropriate, certificates and certifications corresponding to their intervention in the patient's medical care, in accordance with the applicable legal provisions. [45]

And it will consist of:

- Medical history: It must be prepared by medical personnel and other professionals in the health area, in accordance with the specific information needs of each of them, it must have, in the order indicated, the following sections:
 - Interrogation. - It must have at least: identification form, if applicable, ethnic group, hereditary-family history, pathological and non-pathological personal history, current condition (inquire about previous conventional, alternative and traditional treatments) and interrogation by devices and systems (especially ophthalmological).
 - Physical exam. - You must have at least: vital signs (temperature, blood pressure, heart and respiratory rate), weight and height (when applicable).
 - Previous and current results of laboratory, cabinet and other studies (when applicable).
 - Diagnoses or clinical problems (when applicable).
 - Prognosis (when applicable).
 - Therapeutic indication (when applicable).

7.5.3 Eligibility Criteria

It is the assessment that the patient meets all the inclusion criteria and none of the exclusion or elimination criteria.

7.5.4 Assigning Subject Code

It is the granting of a code that represents the subject in the study. This code is assigned when the research subject is included in the study.

7.5.5 Adverse events

Described in the 8. Evaluation and management of adverse events

7.5.6 Vital Signs Measurement

It is the measurement of heart rate, respiratory rate, blood pressure, and body temperature. These measurements can be made with a stethoscope, sphygmomanometer and mercury or digital thermometer.

Vital signs are described in the following sections: 7.4.5.2 Heart rate, 7.4.5.3 Systemic Blood Pressure, 7.4.5.10 Respiratory rate and 7.4.5.11 Body temperature

7.5.7 Urine Pregnancy Test

The pregnancy test will be performed at the baseline visit and at the final visit. The Researcher must provide the research subject with a female, of reproductive age (there is no natural or induced menopause, defined as 12 consecutive months of amenorrhea). To perform the test, the patient will be allowed to go to the bathroom, have privacy for the performance of the test, and after the test is performed, the Investigator must corroborate the result by observing the medical device. [46]

